Children from a public elementary school in Hermosillo, Sonora will be invited to participate in the study. It is worth mentioning that this public school is not representative of all the schools in Hermosillo, Sonora. Hermosillo is a city of about 884,273 inhabitants and around of 392 public elementary schools. It is located in the state of Sonora, in northwestern Mexico. Because the program is entirely online, students who agree to participate will take the intervention from home.

Sample size

No studies of online lifestyle interventions to prevent obesity in schoolchildren during the pandemic were found to obtain the effect size and standard deviation needed to estimate the study sample size. So, we decided that it would be a pilot study of at least 50 participants and no more than 70. This was decided considering our logistical capacity, which implies measuring the response variables at home in a period of 2 weeks, in addition to being able to provide intervention, among other things. The invitation will be made to all students from fourth to sixth grade of a public school in Hermosillo Sonora.

Eligibility criteria

Sign the consent and informed assent and complete the anthropometric measurements and lifestyle questionnaires.

Inclusion criteria

- 4th, 5th and 6th grade students from the participating elementary school.
- Have access to the internet.
- Have an electronic device (eg computer, laptop, tablet or smartphone).
- Nutritional status: normal weight, overweight or obesity.

Exclusion criteria

- Have a medical condition that affects body weight.
- Taking medication that affects body weight.
- Take another intervention that affects body weight.
- Have a condition that prevents physical activity.
- Withdraw informed consent or assent.
- Have a sibling participating in the study.

Implementers

The lifestyle intervention will be implemented by a Nutritionist and two interns from the Bachelor's Degree in Physical Culture and Sports from the study team. In

addition, there will be the support of interns from the Nutritional Sciences Bachelor of the University of Sonora.

Interventions of the study

Online lifestyle intervention

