Secondary outcomes will include the differences in waist circumference, body fat and relative fat mass, physical activity and sedentary lifestyle, quality of life, participation, attendance and nutrition knowledge. The categorical variables such as: food consumption and acceptance, will be evaluated with differences in proportions.

Recruitment

To invite the participants, school directors will first be contacted to invite them, inform them about the objectives and activities of the intervention. Fourth, fifth and sixth grade students from a public elementary school in Hermosillo, Sonora, Mexico will be invited to participate. It will seek to have a space in the students' online school classes, where parents will be invited to attend. A small presentation will be made with the invitation, objectives and activities of the intervention. During the same meeting, they will be sent via chat the link to a web page where they can find the the consent and informed assent and a personal data questionnaire to evaluate inclusion and exclusion criteria. They must be read and signed by parents and children online. Children may participate, even if the parents decide not to get involved in their part of the intervention.

Randomization

The measurements of the study will be carried out in a period of 2 weeks. Once the measurements are completed, the participants who meet the inclusion/exclusion criteria will be randomized to one of two groups: the “online lifestyle intervention” group or the control group. An independent person of the recruitment and

intervention of the study will receive a database, only with the codes and the basic variables of the study (BMI Z-score, sex and age) to perform the allocation of the participants. This will be based on a random block sequence, stratified by BMI Z-score and sex, with an allocation ratio of 1:1. The random number sequence will be generated using the randomization software available on the website: <https://randomizer.org/>. Since the assignment will be made in a single moment and without the knowledge of the participants, its concealment will be guaranteed. Participants will be explicitly informed to the assigned group.

Outcome measures

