- **Personal information.** The first step for the screening of the participants consists of an online questionnaire of personal data. This will be sent at the time of the invitation to the program. Personal data of the child, internet access and electronic device, if they have a disease, if they take medications or perform extra interventions that may affect body weight will be asked. In addition, the email and education leve lof the parents will be asked.

Withdrawal of participants

Participants may withdraw from the study at any time they wish, being able to inform the reason or not.

Statistical Analysis

The normality of the data will be evaluated with the Shapiro Wilk test. Data will be presented as mean and standard deviation (mean \pm SD) or median and interquartile ranges according to their distribution. An independent samples t-test or Mann-Whitney U test will be used to analyze the difference in BMI Z-score and changes in secondary outcomes between groups. A chi-square test will be used to make comparisons on categorical variables. Two-tailed tests with $p \leq 0.05$ will be used as the criterion for statistical significance.

Data will be analyzed with an intention-to-treat analysis. If participants decide to withdraw from the intervention, they will be asked if the measurement at 4 months can be obtained to have at least the primary outcome for inclusion in the intention-to-treat analysis. If data is not obtained for any reason or subjects were excluded due to a protocol violation, they will be replaced by their baseline measurement.

Results will focus on change in the primary study variable (BMI Z-score), while changes in secondary variables and sub-analyses (sex and BMI: normal, overweight/obese) will be considered exploratory only. For data analysis, NCSS version 10 software (Number Cruncher Statistical System for Windows, Kaysville, UT, USA) will be used.

Confidentiality

Identifiable information and will be kept confidential. Each participant will be assigned a code, therefore, their identifiable information will appear with that code and not with names. Only the physical files will keep the names, which will be kept by the principal investigator of the study, in a safe place. Only the study team may have access to the database, for their purposes.

Declaration of interest

The authors did not report any potential conflicts of interest.

REFERENCES

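### Exploratory sub-analyses by sex and BMI category have no stated test of whether the effect differs between subgroups; an arm-by-subgroup model would supply one at almost no cost

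*Combined protocol and SAP*

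**What the plan says.** In the combined protocol and SAP, the Statistical Analysis section gives the comparison methods in two sentences: "An independent samples t-test or Mann-Whitney U test will be used to analyze the difference in BMI Z-score and changes in secondary outcomes between groups", and "A chi-square test will be used to make comparisons on categorical variables". One criterion covers everything: "Two-tailed tests with $p \leq 0.05$ will be used as the criterion for statistical significance". The same section focuses the results on BMI Z-score and adds that "sub-analyses (sex and BMI: normal, overweight/obese) will be considered exploratory only".

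It does not say how the sub-analyses will be carried out or read. No regression or ANCOVA model and no interaction term appears anywhere in the document.

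Under Randomization, allocation is "stratified by BMI Z-score and sex", with no cut-points given for the BMI Z-score strata. Under Sample size, the trial is a "pilot study of at least 50 participants and no more than 70", and the reason given is practical: "This was decided considering our logistical capacity". That section also says that no effect size or standard deviation was available.

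**The concern.** A subgroup analysis asks whether the effect of the intervention differs between, for example, boys and girls. The named tests compare two arms. Applied inside each subgroup, they give one p-value per subgroup and no comparison between subgroups. If one p-value falls below 0.05 and the other does not, the difference in effect has still not been tested.

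In a trial of 50 to 70 children each subgroup is small, so such split results are expected even when the effect is the same in both. The Study design section presents the pilot as preparation for a definitive trial. An apparent effect in only one sex or one BMI category could be carried into the thinking about that trial, although no section says that subgroup results will be used that way.

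**Working it through.** The plan states no power, effect size or SD, so there is no figure of its own to reproduce.

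**Inputs from the documents**
- Total N of 50 to 70 (Sample size), allocated 1:1 (Study design), so 25 to 35 per arm.
- Two-sided 0.05, with no separate level for sub-analyses (Statistical Analysis).
- All randomised children are counted, because missing values are replaced by baseline (Statistical Analysis).

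**Assumptions**
- The same standardised effect d in both subgroups, from 0.2 to 0.8 SD of the change in BMI Z-score.
- An even split for sex.
- For BMI, either an even split or 35.5% overweight/obese. The latter is the national figure in the Introduction, which may not fit this school.
- Arms balanced within subgroups, and normally distributed data.

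**Cell sizes per arm**
- Even split: 25 × 0.5 = 12.5 to 35 × 0.5 = 17.5, so about 12-18.
- 35.5/64.5 split, overweight/obese: 25 × 0.355 = 8.9 to 35 × 0.355 = 12.4, so about 9-12.
- 35.5/64.5 split, normal weight: 25 × 0.645 = 16.1 to 35 × 0.645 = 22.6, so about 16-23.

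**Formulas**
- With m children per arm in a subgroup, the t statistic has noncentrality d × √(m/2) and 2m − 2 degrees of freedom. This gives the subgroup power.
- The two subgroups are disjoint, so with powers a and b: P(exactly one significant) = a(1 − b) + b(1 − a).

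**Worked case** (N = 50, even split, d = 0.5): noncentrality = 0.5 × √6.25 = 1.25, so a = b = 0.224. P(exactly one) = 2 × 0.224 × 0.776 = 0.348.

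**Probability that exactly one subgroup is significant under a uniform effect**

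| N | Split | d = 0.2 | d = 0.3 | d = 0.5 | d = 0.8 |
|---|---|---|---|---|---|
| 50 | 50/50 | 14% | 20% | 35% | 50% |
| 50 | 35.5/64.5 | 14% | 20% | 35% | 53% |
| 70 | 50/50 | 16% | 24% | 42% | 47% |
| 70 | 35.5/64.5 | 16% | 24% | 43% | 51% |

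In between, at N = 60 with an even split and d = 0.7, each subgroup has 46% power and exactly one is significant in 50% of trials. With no effect at all the figure is 2 × 0.05 × 0.95 = 9.5% per factor.

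**Interaction test.** Under a uniform effect it rejects in about 5% of trials per factor (4.9-5.1% in a simulation of 40,000 trials per scenario). At d = 0.5-0.8, only 8-13% of the split patterns came with a significant interaction.

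**Power of the interaction test.** The standard error of the difference between two subgroup effects, in SD units with an even split, is √(4/m). That is √(4/12.5) = 0.566 at N = 50 and √(4/17.5) = 0.478 at N = 70. If the true effects differ by 0.5-0.8 SD, power at two-sided 0.05 runs from about 14% (0.5 SD, N = 50) to about 38% (0.8 SD, N = 70), before any gain from baseline adjustment.

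**The case against.** The strongest reply is that the plan neither says that it will test within subgroups nor plans to conclude that effects differ. That stands. Within-subgroup testing is an inference from the absence of any other method. A reader might go further and infer that the protocol commits to separate subgroup p-values, or intends to claim an effect in one subgroup only. The documents support neither reading.

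The plan also limits the consequence itself. Results focus on the primary variable, the sub-analyses are labelled exploratory, there are only two prespecified factors, and no listed objective concerns subgroups. This keeps the point minor. It does not remove it, because the label lowers the weight of a result without making the named tests compare effects.

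Setting 35-53% beside 5% compares a pattern of results with a formal error rate, and the pattern misleads only if it is read as a difference. That is fair. The comparison shows how often the opportunity for misreading arises, not how often the investigators would misread.

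The size also depends on an effect that the documents do not give. At 0.2-0.3 SD the figure is 14-24%, so a flat statement that split results will be frequent would be too strong.

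A reader might also take the randomisation strata to be the same as the subgroups. Without cut-points the text does not show this.

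Finally, the interaction test has little power here, and a non-significant result could itself be misread as equal effects. The report needs to guard against that.

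**Conclusion.** The point holds in limited form. The plan announces sub-analyses by sex and BMI category, but none of its named methods tests whether the effect differs between subgroups. Carried out with those methods, the sub-analyses would produce separate p-values that do not answer the subgroup question.

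For each factor, a uniform effect would give a split result in about 14-24% of trials if the effect is small and about 35-53% if it is moderate to large. These figures rest on the assumed effect sizes, subgroup splits and within-arm balance, and on the inference that the named tests would be applied within subgroups. The primary analysis is not affected. Given the exploratory status, this is a refinement worth making and not a flaw in the trial's main conclusion.

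**What to change.** Add a short statement to the Statistical Analysis section:

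- For sex, and separately for baseline BMI category (normal versus overweight/obese), fit one model for the 4-month BMI Z-score with arm, baseline BMI Z-score, the subgroup factor and the arm-by-subgroup interaction.
- Report the interaction estimate with its 95% CI.
- Show the effect in each subgroup with its CI, without within-subgroup significance claims.
- Keep the exploratory label.
- State that interaction power is low, so a non-significant interaction does not show that the effects are equal.

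The cost is a few lines of text. Sex and baseline BMI are already collected, and the BMI category in the model need not match the randomisation strata. No child, visit or measurement is added, and the primary analysis stays as it is. This is a free improvement.
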